-44, 1, 28	6	Left	Precentral gyrus	fMRI	Initiation of voiding	[name] 2014
2, -32, 66	4	Right	Superiomedial precentral	PET	Voiding	Blok/Holstege 1997 
-6, -26, 74	4	Left	Superiomedial precentral	PET	Voiding	Blok/Holstege 1997 
Non-neurogenic voiding dysfunction						
54, -4, 6	6	Right	Precentral	fMRI	Urethra	Fowler 2010 
Neurogenic voiding dysfunction (MS)						
-39, 34, 5	45	Left	IFG	fMRI	Initiation of voiding	[name] 2017
38, 33, 6	45	Right	IFG	fMRI	Voiding	[name] 2017

[figure not shown]
Table 1: MNI: Montreal Neurological Institute coordinates; BA: Brodmann Areas; HA: Hemisphere; PF: Pelvic Floor

In a small group of women with urinary retention, due to urethral sphincter dysfunction, *peripheral nerve* neuromodulation modified the activity of the right postcentral gyrus, precentral/temporal, and inferior temporal regions. fMRI studies report that medial prefrontal cortex and supplementary motor areas are the main cortical regions involved in pelvic floor contraction, and could be used to phenotype responders versus non-responders to biofeedback assisted pelvic floor physical therapy in overactive bladder patients.

- Aims 1 and 2 of this proposal characterize specific brain regions that are activated during voiding in MS and these regions will be added to the current data (table 1) to individualize the targets used in aim 3 for multi-site transcranial modulation.

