- Measure fractional anisotropy (FA) and mean diffusivity (MD) of the ATR and SLF in Groups 1a, 1b, and 2.
- Assess whether damage to SLF or ATR are associated with voiding dysfunction in our patient population.

**Specific Aim 3: Targeted cortical stimulation in Group 1 causes changes in ROI (identified during specific aim1) that better recapitulate the activation patterns in group 2 or HCs by:**

- Assessing BOLD and FC activation in the ROIs following individualized TRPMS in patients in Group 1.
- Evaluating voiding improvement via UDS and validated questionnaires following TRPMS.

- c) Identifying baseline clinical/UDS or neuroimaging factors that could predict response to TRPMS.
- d) Evaluating EMG changes in the pelvic floor following TRPMS.

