## EXPERIMENTAL PLAN AND FEASIBILITY

We have completed and recently published a well-powered study, on twenty-seven female MS patients, that evaluated brain response to bladder filling during the bladder *storage phase*. Aims 1 and 2 are retrospective analysis of the *voiding phase* from our extensive and meticulously collected neuroimaging raw data available to us from our prior completed cohort. Aim 3 is a small, pilot feasibility study (n=8).

**Study duration:** Based on our experience, we anticipate that one year will allow appropriate time for data analysis for Aims 1 and 2. An additional (concurrent) 1-2 years will allow for appropriate patient recruitment, performance of the protocols, and data evaluation for Aim 3.

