## Endpoints

### Primary Endpoint

- a) BOLD signal intensity and FC pattern in *a priori selected* ROIs at “initiation of voiding” in MS patients.
- b) BOLD and FC pattern changes following TRPMS.

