## Description of interventions

**Subject Evaluations:** Each patient will undergo a detailed history and physical examination with the following assessments: Demographic Form, American Urological Association Symptom Score (AUASS), Neurogenic

Bladder Symptom Score (NBSS), MRI Safety Screening Questionnaire, Hospital Anxiety and Depression Scale, and Expanded Disability Status Scale. AUASS and NBSS both include questions regarding the voiding phase and are validated in neurogenic patients. Postvoid residual urine, urinalysis, urine culture, and pregnancy (if applicable) will be assessed prior to the MRI scan. A clinical UDS will be performed within 10 years prior to the neuroimaging scan. Consent will be signed during the first visit. High density Electromyography (EMG) will be performed at the beginning of the first and the last sessions of TRPMS treatment however this is an optional testing and patients can refuse to participate in the EMG testing. Patients from Group 1 who participate in the TRPMS will undergo a repeat fMRI scanning following the completion of the therapy. In addition their symptoms will be assessed with repeat UDS and validated questionnaires.

After their post TRPMS Intervention Fmri visit, subjects will return to the clinic to complete 4 months (+/- 1 month) and 12 months (+/-1 month) follow up visits. At these follow-up visits, they will completing validated questionnaires, uroflow testing and PVR scan.

**Simultaneous UDS/fMRI:** Double lumen 7 French MRI-compatible catheters are placed in the bladder and rectum. Either 3T or 7 T full body MRI scanner with standard 12 channel head coil is used. Instructions to communicate using right hand signals representing “strong desire to void” and “voiding” are given. In order to keep our noise-to-signal ratio low, all stimulators including any extra visual stimuli and the UDS machine are removed from the MRI room. Filling and voiding cycles are repeated up to 4 times in each patient. If the patient is unable to void, then the bladder will be drained passively.

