**Transcranial Rotating Permanent Magnet Stimulator (Aim 3 only):** We will use the data obtained in Aim 1 to further identify superficial cortical targets for intervention in each patient with voiding dysfunction and we will construct an individualized therapeutic cap to deliver repeated 100 – 500 ms stimuli at 0.02 Hz for 40 min each week day for 2 weeks (based on our preliminary TRPMS data in other neurological disorders). As discussed in the Innovation section of this proposal, TRPMS is safe, precisely programmable, inexpensive, and can modulate multiple areas of the brain at the same time, making it an ideal modality for our proposal.

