**Power Analysis:** fMRI studies suggest that approximately 12 subjects are required to achieve 80% power at the single voxel level for typical activations, while accounting for intra-and inter-subject variability. Most fMRI studies, evaluating bladder function have included 8-12 subjects. For this proposed study, we account for 10% exclusions due to movement artifact and anticipate 13 patients for groups 1 and 2, with total of N=26.

(Recruitment and scanning is already completed for Aims 1 and 2, data analysis is pending funding). Aim 3 is a small pilot feasibility study and we propose N=8.

**Limitations of the study and alternative strategies:** The primary strength of this study is the simultaneous neuroimaging and UDS platform which includes the voiding or attempt to void phase. However, limitations do exist: voiding dysfunction is heterogeneous and dynamic and variations within studies may exist. Our patient population represents only a subset of a larger and more complex group and may have inter and intra-subject variability. Although patients with MS are generally accustomed to UDS and MRIs, combined UDS/fMRI may create anxiety and non-physiologic state. Furthermore, voiding supine may pose a challenge to many individuals who can void spontaneously while seated. The repetition of the filling and voiding task four times is an attempt to provide a high enough level of signal to evaluate the fMRI data. This provides a rich dataset that can be analyzed to infer information about the brain at initiation of voiding. Additionally, by preselecting our ROIs and WMTs we increase our specificity; however we may miss other important brain centers/pathways.

Direct comparisons between the current TRPMS prototype that we plan to use and a commercially used conventional TMS coil show that the maximum voltage induced in an inductor by the former (12 - 30 V/m) is about 6% of the maximum machine output of the latter (200 - 500 V/m). Although this lower voltage has added advantages of portability, multi-site stimulation capability, and significantly lower side effects such as heat, seizure activity, or headaches, it may raise a concern of not being strong enough to have an effect in our patients. Alternatively we may add to the stimulated targets or consider selecting only one region and use the commercially available TMS for our next trial.

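### Aim 3 words an uncontrolled before-after scan in 8 treated patients as a causal shift toward either of two references, and does not say which scan selects each patient's targets

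*Combined protocol and SAP*

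**What the plan says.** - **Claim.** Under Objectives/Specific Aims/Hypotheses, Specific Aim 3 says that stimulation of Group 1 "causes changes in ROI (identified during specific aim1) that better recapitulate the activation patterns in group 2 or HCs by" a list of assessments.
- **Evidence.** Under Description of interventions: "Patients from Group 1 who participate in the TRPMS will undergo a repeat fMRI scanning following the completion of the therapy". No sham, untreated or repeat-baseline comparison is described. The scanner may be 3T or 7T, and the plan does not require the same field strength before and after.
- **Size and status.** The Power Analysis paragraph states: "Aim 3 is a small pilot feasibility study and we propose N=8". No effect size, variance or test accompanies that number.
- **Endpoint.** The second primary endpoint is "BOLD and FC pattern changes following TRPMS". Neither the Endpoints section nor Data Collection and Statistical Analysis gives a measure of resemblance, a test of pre/post change, or a choice between Group 2 and healthy controls.
- **Targets.** The TRPMS paragraph says: "We will use the data obtained in Aim 1 to further identify superficial cortical targets for intervention in each patient with voiding dysfunction". The Innovation section says of the regions found in Aims 1 and 2 that "these regions will be added to the current data (table 1) to individualize the targets used in aim 3". The Experimental Plan describes Aims 1 and 2 as a retrospective analysis of "neuroimaging raw data available to us from our prior completed cohort", while Aim 3 has its own recruitment period.
- **Limitations.** The limitations paragraph mentions neither the absence of a comparison nor regression to the mean.

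**The concern.** A before-after difference in treated patients contains everything that changes between two scans, and only part of that, if any, is due to TRPMS. Patients may be less anxious at a second scan, MS bladder symptoms fluctuate, extreme values drift back toward the average, and the field strength may differ. The verb *causes* attributes the whole difference to the device.

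Two further features make a favourable reading easier. The success pattern is Group 2 *or* healthy controls, so there are two ways to succeed. And targets are individualised. If a region is chosen because it looks abnormal on a scan, and the same scan supplies the baseline value, that region will on average look more normal next time with no treatment effect.

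What is at stake is the interpretation of primary endpoint (b). The Transition Plan says the data will supply the rationale for multicentre efficacy trials, so an apparent normalisation would be carried forward as evidence that stimulation works.

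**Working it through.** **1. The plan's own number.** N=8 has no stated inputs, so there is nothing to reproduce. For scale, a paired two-sided 5% t-test with n=8 has 80% power only for a mean change of about 1.16 SD of the changes.

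**2. Which scan selects the targets?** Three readings fit the text.
- *The patient's own pre-treatment scan selects the targets and supplies the baseline.* The TRPMS paragraph permits this (targets in each patient, an individualised cap) but does not say it.
- *An earlier Aim 1 scan of the same patient selects them and a fresh scan supplies the baseline.* Selection and baseline are then separate.
- *The completed cohort and Table 1 supply them.* The Innovation section and the Experimental Plan allow this, and for newly recruited patients selection then adds no regression to the mean.

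The calculation in step 3 applies to the first reading only.

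**3. Size of the bias under the first reading.** Assumptions, none of them in the documents: each of k candidate regions has true deviation T ~ N(0, ICC) from the reference; each scan gives Y = T + e with e ~ N(0, 1 - ICC); there is no treatment effect. The target is the region with the largest |Y| at baseline. The score is D = |Y_post| - |Y_pre| in that region, tested by a paired t-test on 8 patients. A significant fall in distance should occur in 2.5% of studies. Results from 20,000 simulated studies per cell:

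| ICC | k = 2 | k = 5 |
|---|---|---|
| 0.3 | 16% | 58% |
| 0.5 | 14% | 48% |
| 0.7 | 12% | 32% |
| 0.8 | 10% | 24% |

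Two candidates is the case closest to the plan: of the five a priori ROIs, only the inferior frontal and precentral gyri are cortical. Five cortical candidates would require drawing on Table 1. A true Group 1 offset of 0.5 SD changes little (13% instead of 14% at ICC 0.5, k = 2). When a separate scan selects the target, the rate is 2.2-2.7% throughout.

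**4. Either of two references.** With fixed ROIs, no effect and patterns of 2 or 5 ROIs, the chance of a significant shift toward at least one reference is 2.4-2.6% if both references lie in the same direction from Group 1, 4.0-5.0% if the directions are orthogonal, and 4.7% if they are opposite. One named reference gives about 2.5%.

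**5. Is splitting the baseline cycles enough?** Filling and voiding are repeated up to 4 times, so one half could select the target and the other half supply the baseline.
- If all noise is specific to a cycle and cycle counts are equal before and after, the rate returns to about 2.5%.
- A half-session baseline against a full-session post value, scored on distance, leaves 3-8%, because the noisier baseline lies further from the reference.
- If half of the noise is shared within a session (assumed), about 6-14% remains on a change signed by the direction of the baseline deviation.

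**6. Is Group 2 usable as the reference?** Group 1 includes patients with postvoid residual of at least 20% of maximum cystometric capacity; Group 2 includes spontaneous voiders below 40%. A spontaneous voider at 30% meets both definitions.

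**The case against.** The strongest reply is that Aim 3 is labelled a pilot feasibility study, the overall hypothesis says only that modulation may be feasible, efficacy is deferred to later trials, and primary endpoint (b) speaks of changes following TRPMS, which is already close to the wording requested here. This stands as a reason not to demand a powered or sham-controlled design. It does not cure the aim: pre/post change is listed as a primary endpoint, the aim attributes it causally, and the result is meant to justify efficacy trials.

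A second reply is that target selection may create no bias at all. That is correct if targets come from the completed cohort and the literature. A reader might infer that each patient's own baseline scan picks the targets, but the documents do not say so, nor that the most abnormal region is chosen. What stands against the plan is its silence on the point.

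A reader might also infer a false-positive rate above one half. At ICC 0.5, a change signed by the direction of each patient's own baseline deviation does give 56% with five candidates and about 32% with two. The plan states no such score; on distance from the reference the figures are 48% and 14%, and both still need same-scan selection.

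Likewise, the two references might be thought to double the error across five ROIs, from 1 - 0.975^5 = 11.9% to 1 - 0.95^5 = 22.6%. That is a ceiling, which needs five independent ROIs and references on opposite sides of Group 1 in each.

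**Conclusion.** The point holds in a limited form. What is certain from the text is that Aim 3 makes a causal claim which one repeat scan in 8 treated patients, without a comparison, cannot support, and that neither a single reference nor a measure of resemblance is named.

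What is conditional is the selection bias. If the pre-treatment scan also selects the targets, the false-positive rate on distance is about 10-16% with two cortical candidates and 24-58% with five, against 2.5%. These figures rest on the assumed ICC of 0.3 to 0.8, most-deviant selection and no true group offset; the documents give no reliability, variance or number of candidates. The two-reference choice is a smaller matter, at most 5% against 2.5% per pattern.

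The documents do not support saying that Aim 3 will show normalisation regardless of effect, or that the pilot is without value as a feasibility study.

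**What to change.** 1. **Wording.** Replace *causes changes* with *is followed by changes*, and limit the Aim 3 conclusion to feasibility and description. The analysis changes below do not make the design causal, so this one is essential.
2. **ROIs.** Make the primary pre/post score the change in the fixed a priori ROIs listed for Aim 1, chosen without using the Aim 3 pre-treatment scan. State which scan selects targets. If individually selected ROIs are also scored, take selection and baseline value from different data, use equal cycle counts before and after, and state that noise shared within a session may leave some bias.
3. **Reference.** Name Group 2 as the single primary reference with one stated measure of change, and make healthy controls secondary. First reconcile the Group 1 and Group 2 definitions, which overlap from 20% to below 40% postvoid residual.
4. **Internal comparison.** Report stimulated minus unstimulated ROIs as supportive only: the Innovation section says TRPMS also modulates connections between areas, so unstimulated regions are not a clean control.

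The cost is text and analysis specification, with no added scans. The price is a more modest claim and, where cycles are split, a noisier baseline for individually selected ROIs. Splitting also needs at least two completed cycles per patient, which the plan does not guarantee.

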## EXPERIMENTAL PLAN AND FEASIBILITY

We have completed and recently published a well-powered study, on twenty-seven female MS patients, that evaluated brain response to bladder filling during the bladder *storage phase*. Aims 1 and 2 are retrospective analysis of the *voiding phase* from our extensive and meticulously collected neuroimaging raw data available to us from our prior completed cohort. Aim 3 is a small, pilot feasibility study (n=8).

**Study duration:** Based on our experience, we anticipate that one year will allow appropriate time for data analysis for Aims 1 and 2. An additional (concurrent) 1-2 years will allow for appropriate patient recruitment, performance of the protocols, and data evaluation for Aim 3.

## Endpoints

### Primary Endpoint

- a) BOLD signal intensity and FC pattern in *a priori selected* ROIs at “initiation of voiding” in MS patients.
- b) BOLD and FC pattern changes following TRPMS.

### Secondary Endpoints

- a) FA and MD of ATR and SLF white matter tracts in Groups 1 and 2.
- b) Clinical scores: UDS parameters, urinary symptom scores, surveys at baseline and following TRPMS.
- c) BOLD signal characteristics and FC patterns in ROIs in patients with versus without DSD.

## Selection and Recruitment of the Subject

**Inclusions:** Adult female patients with clinically stable MS [Expanded Disability Status Score (EDSS)  $\leq 6.5$ ], with bladder symptoms  $\geq 3$  months, will be screened. Patients will be considered to have VD if they have an increased Postvoid Residual ( $\geq 20\%$  Maximum Cystometric Capacity) or abnormally slow and /or incomplete micturition based on abnormally slow urine flow rates. Patients who perform self-catheterization will be included in the VD category as well.

Patients with active UTI can be treated and subsequently screened for the trial.

**Regarding patients with DSD:** Appropriately placed and traced perineal surface electrodes used for EMG recordings can be used to determine presence or absence of DSD. There is no clear cutoff or consensus for the amount of EMG activity change during the voiding phase. We will use increased EMG activity by 20% during detrusor contraction (voiding), in the absence of valsalva maneuvers, to determine DSD.

**Exclusions:** Men, anatomical bladder outlet obstruction (anti-incontinence procedures, urethral strictures, or advanced pelvic organ prolapse). Severe debilitating MS, history of seizures, pregnancy or planning to become pregnant, contraindications to MRI, history of augmentation cystoplasty, presence of other neurological disorders besides MS.

**Relevant biological variables (sex):** At this point, males are excluded from our evaluation to avoid potential confounding factors by common bladder outlet pathologies secondary to benign or malignant prostatic pathology, primary bladder neck obstruction, and urethral strictures (all common in men). In addition posture during urination (lying flat in the scanner versus sitting or standing) appears to affect voiding and this difference is more noticeable in males versus females, especially when bladder symptoms are present. Due to these differences between sexes and the possibility of them being confounding factors at this point we are excluding males.

**Subject recruitment:** Our Neurourology Clinic where I serve as the clinical director, has three fulltime fellowship trained urologists and is a referral center in Houston. My mentor and chairman [name] is a nationally recognized clinician in this field. Eligible patients for our study will be screened and recruited from our clinic.

## Description of interventions

**Subject Evaluations:** Each patient will undergo a detailed history and physical examination with the following assessments: Demographic Form, American Urological Association Symptom Score (AUASS), Neurogenic

Bladder Symptom Score (NBSS), MRI Safety Screening Questionnaire, Hospital Anxiety and Depression Scale, and Expanded Disability Status Scale. AUASS and NBSS both include questions regarding the voiding phase and are validated in neurogenic patients. Postvoid residual urine, urinalysis, urine culture, and pregnancy (if applicable) will be assessed prior to the MRI scan. A clinical UDS will be performed within 10 years prior to the neuroimaging scan. Consent will be signed during the first visit. High density Electromyography (EMG) will be performed at the beginning of the first and the last sessions of TRPMS treatment however this is an optional testing and patients can refuse to participate in the EMG testing. Patients from Group 1 who participate in the TRPMS will undergo a repeat fMRI scanning following the completion of the therapy. In addition their symptoms will be assessed with repeat UDS and validated questionnaires.

After their post TRPMS Intervention Fmri visit, subjects will return to the clinic to complete 4 months (+/- 1 month) and 12 months (+/-1 month) follow up visits. At these follow-up visits, they will completing validated questionnaires, uroflow testing and PVR scan.

**Simultaneous UDS/fMRI:** Double lumen 7 French MRI-compatible catheters are placed in the bladder and rectum. Either 3T or 7 T full body MRI scanner with standard 12 channel head coil is used. Instructions to communicate using right hand signals representing “strong desire to void” and “voiding” are given. In order to keep our noise-to-signal ratio low, all stimulators including any extra visual stimuli and the UDS machine are removed from the MRI room. Filling and voiding cycles are repeated up to 4 times in each patient. If the patient is unable to void, then the bladder will be drained passively.

**Transcranial Rotating Permanent Magnet Stimulator (Aim 3 only):** We will use the data obtained in Aim 1 to further identify superficial cortical targets for intervention in each patient with voiding dysfunction and we will construct an individualized therapeutic cap to deliver repeated 100 – 500 ms stimuli at 0.02 Hz for 40 min each week day for 2 weeks (based on our preliminary TRPMS data in other neurological disorders). As discussed in the Innovation section of this proposal, TRPMS is safe, precisely programmable, inexpensive, and can modulate multiple areas of the brain at the same time, making it an ideal modality for our proposal.

